7.2. Secondary Efficacy Analyses

7.2.1. Rate of exacerbations

Rate of exacerbation is defined as the frequency of exacerbations (subsequent to the index exacerbation) within the specified time period, for example, the 12-Week Treatment Period or the 24-Week Study Period.

The length of time on treatment or in study, depending on the specified time-period, for each participant will be calculated for each endpoint as follows:

Endpoint	Time period	Length of time derivation
Rate of (on-treatment) exacerbations, summarised by: 
 • Moderate/severe exacerbations • Moderate exacerbations • Severe exacerbations • All (mild, moderate and 	12-Week Treatment Period	Time from date of randomisation to date of last dose of study treatment

Endpoint	Time period	Length of time derivation
severe) exacerbations		
Rate of (on-or off-treatment) exacerbations, summarised by: 
 • Moderate/severe exacerbations • All exacerbations 	12-Week Treatment Period	Time from date of randomisation to Day 84 (Visit 6) Visit Date. For participants who withdraw early from the study: Time from date of randomisation to date of study withdrawal
Rate of (off-treatment) exacerbations, summarised by: 
 • Moderate/severe exacerbations • Moderate exacerbations • Severe exacerbations 	12-Week Follow Up Period	Time from date of last dose of study treatment to date of study withdrawal/completion
Rate of (on- and off- treatment) exacerbations, summarised by: 
 • Moderate/severe exacerbations • Moderate exacerbations • Severe exacerbations 	Full 24-Week Study Period	Time from date of randomisation to date of study withdrawal/completion

Refer to Section 13.5 for further details regarding the length of time derivation

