7.2.1.1. Statistical analyses

The rate of exacerbations will be analysed using a Bayesian generalized linear model assuming a negative binomial distribution for the underlying exacerbation rate with a log link function. An offset to account for the length of time on treatment or in study, depending on the specified time-period, for each participant (as described above) will be included in the model as \log_e (length of time).

Non-informative priors will be used for all modelling parameters. Wherever possible conjugate priors will be utilised.

The median exacerbation rates for each dose arm per 12 weeks, along with the median ratio in exacerbation rates (nemiralisib/placebo) per 12 weeks for each dose, will be estimated and corresponding 95% HPD credible intervals presented. The probability that the true exacerbation rate ratio is less than 1, in addition to other values appropriately selected based on the data, will be presented.

Based on pharmacological predictions, the 500 mcg and 750 mcg doses are expected to result in similar levels of target inhibition and thus potentially translate to similar clinical benefit, therefore estimates of the exacerbation rates for pooled data from 500 mcg plus 750 mcg will also be presented.

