7.2.5. EXacerbations of Chronic Pulmonary Disease Tool - Patient Reported Outcome (EXACT)

The EXACT is a 14-item daily diary designed to provide a measure of patient-reported symptoms of COPD exacerbation. An EXACT Total Score, ranging from 0 to 100, where

higher scores indicate a more severe condition, will be derived for each day of diary collection according to the instructions in the EXACT User Manual (Version 8.0, [Evidera, 2016](#)).

The electronic EXACT diary does not allow a study patient to skip individual items, therefore no missing data are expected for individual items. However, if missing values occur for individual items, the Total Score that contains the item will be set to missing for that day. Moderate-to-severe COPD patients are expected to experience symptom(s) each day, and a score of zero on all 14 EXACT items is likely to represent a situation where in order to complete the diary quickly, the respondent did not accurately report their daily symptom(s), therefore if the EXACT Total Score is 0, it will be set to missing.

A 3-day Rolling Average EXACT Total Score will be calculated for each day, X, as:

$$\frac{(\text{EXACT Total Score on Day X-1} + \text{EXACT Total Score on Day X} + \text{EXACT Total Score on Day X+1})}{(\text{Number of days with non-missing values})}$$

Note, for Day 1, the Rolling Average EXACT Total Score will be calculated as the average of EXACT Total Score on Days 1 (Randomisation) and 2 only, since no EXACT data is collected prior to randomisation. Similarly, the Rolling Average EXACT Total Score for the last study day will be calculated as the average of EXACT Total Score on the last day and on the day before the last day.

The Rolling Average EXACT Total Score will be calculated for each day as long as at least 1 EXACT total score in the sequence is present. Therefore, only in the case where EXACT total scores are missing for 3 consecutive days in a row (or 2 consecutive days in the case of the first and last day rolling average calculation), will the rolling average score be missing.

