The Maximum Observed Value (MOV) is defined as the highest Rolling Average EXACT Total Score observed within the first 14 days of randomisation. Note: this definition differs from the definition in the EXACT User Manual of "the highest rolling average EXACT score observed in the context of an EXACT exacerbation within the first 14 days of the exacerbation", since the date of the index exacerbation is likely to be prior to randomisation.

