7.2.5.1. Proportion of participants achieving EXACT-defined recovery from index exacerbation

EXACT-defined recovery from the index exacerbation is defined as a decrease in the Rolling Average EXACT Total Score ≥ 9 points from the Maximum Observed Value, sustained for ≥ 7 days, with the first of the 7 days defined as the recovery day.

The proportion of participants achieving EXACT-defined recovery from the index exacerbation by Days 14, 28, 56, and 84 will be calculated as:

$$\frac{(\text{Number of participants who experience an EXACT-defined recovery on or before Day X})}{(\text{Total number of participants in the MITT population})}$$

Where Day X is 14, 28, 56, and 84.

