7.2.5.4. Statistical analyses

The proportion of participants achieving EXACT-defined recovery from the index exacerbation will be analysed using a Bayesian logistic regression model. Separate models will be fitted for each time-point.

Non-informative priors will be used for all modelling parameters. Wherever possible conjugate priors will be utilised.

The results of the analysis will be presented in terms of odds ratios together with its associated 95% HPD credible interval. The probability that the true odds ratio is greater than 1, in addition to other values appropriately selected based on the data, will be presented.

Time to EXACT-defined recovery from index exacerbation will be analysed using the same techniques as described in Section 7.2.2.1.

Severity of subsequent HCRU-defined exacerbation(s) defined by EXACT will be summarised for each treatment group and reported by study period. The severity of subsequent HCRU-defined exacerbation(s) occurring whilst a participant is on treatment will be reported as during the 12-Week Treatment Period and the severity of subsequent HCRU-defined exacerbation(s) occurring after the last dose of study treatment will be reported as during the 12-Week Follow-up Period.

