13.3.2. Study Phases

Exacerbation events during the 12-Week Treatment Period will be classified according to their occurrence from randomisation until treatment discontinuation/study withdrawal days, as detailed below.

Study Phase	Occurring from randomisation until
On-Treatment during the 12-Week Treatment Period	Treatment Stop Day
On- or Off-Treatment during the 12-Week Treatment Period	Day 84 or Study Withdrawal Day if Treatment Stop Day is < Day 84

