2.27.	MITT	Example 5	Summary of On-treatment (Moderate/Severe) Subsequent Exacerbations		EOT, SAC
2.28.	MITT	Example 5	Summary of On-treatment (Mild/Moderate/Severe) Subsequent Exacerbations		SAC
2.29.	MITT	Example 5	Summary of On-treatment (Moderate/Severe) Subsequent Exacerbations by Index Exacerbation Severity		EOT, SAC
2.30.	MITT	Example 6	Statistical Analysis of On-treatment (Moderate/Severe) Subsequent Exacerbations		EOT, SAC
2.31.	MITT	Example 6	Statistical Analysis of On-treatment (Mild/Moderate/Severe) Subsequent Exacerbations		SAC
2.32.	MITT	Example 6	Subgroup Analysis of On-treatment (Moderate/Severe) Subsequent Exacerbations by Index Exacerbation Severity		EOT, SAC
2.33.	MITT	Example 5	Summary of On-treatment Subsequent Exacerbations by Index Exacerbation Type		SAC

Efficacy: Tables					
No.	Population	IDSL / Example Shell	Title	Programming Notes	Deliverable [Priority]
2.34.	MITT	Example 5	Summary of On-treatment Subsequent Exacerbations by Number of Exacerbations in Previous 12 Months		SAC
2.35.	MITT	Example 5	Summary of On-treatment (Moderate/Severe) Subsequent Exacerbations by Baseline Maintenance Therapy		EOT, SAC
2.36.	MITT	Example 6	Subgroup Analysis of On-treatment (Moderate/Severe) Subsequent Exacerbations by Baseline Maintenance Therapy		EOT, SAC
2.37.	MITT	Example 5	Summary of On-treatment (Moderate/Severe) Subsequent Exacerbations by Baseline ICS Therapy		EOT, SAC
2.38.	MITT	Example 6	Subgroup Analysis of On-treatment (Moderate/Severe) Subsequent Exacerbations by Baseline ICS Therapy		EOT, SAC
2.39.	MITT	Example 6	Subgroup Analysis of On-treatment (Moderate/Severe) Subsequent Exacerbations by EXACT Recovery Status at Day 14		EOT, SAC
2.40.	MITT	Example 12	Summary of Number of On-treatment Subsequent (Moderate/Severe) Exacerbations Treated with Steroids/Antibiotics		EOT, SAC
2.41.	MITT	Example 6	Subgroup Analysis of On-treatment (Moderate/Severe) Subsequent Exacerbations by Baseline Blood Biomarker Status		EOT, SAC
2.42.	MITT	Example 5	Summary of On-or Off-treatment (Moderate/Severe) Subsequent Exacerbations During the 12-Week Treatment Period		SAC
2.43.	MITT	Example 5	Summary of On-or Off-treatment (Mild/Moderate/Severe) Subsequent Exacerbations During the 12-Week Treatment Period		SAC
2.44.	MITT	Example 5	Summary of On-or Off-treatment (Moderate/Severe) Subsequent Exacerbations During the 12-Week Treatment Period by Index Exacerbation Severity		SAC

Efficacy: Tables					

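### Table 2.39 compares active with placebo within strata of Day 14 EXACT recovery, a post-randomisation outcome, so its rate ratios can be biased if the drug affects recovery or early exacerbations

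*SAP*

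**What the plan says.** SAP Section 13.11.6.3 lists Table 2.39, "Subgroup Analysis of On-treatment (Moderate/Severe) Subsequent Exacerbations by EXACT Recovery Status at Day 14", in the MITT population, for both the End of Treatment interim and final reporting, with no programming note. It uses Example Shell 6, which shows rates by arm, the active-to-placebo ratio with its credible interval, the probability that the ratio is below 1, and the percent reduction. It is therefore a treatment comparison inside each stratum.

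The stratifying variable is defined after randomisation:
- Section 7.2.5.1 defines recovery as a fall of at least 9 points from the maximum observed value, sustained for at least 7 days, "with the first of the 7 days defined as the recovery day".
- Section 7.2.5 takes that maximum as "the highest Rolling Average EXACT Total Score observed within the first 14 days of randomisation".
- The rolling average is centred. Its sum starts at "EXACT Total Score on Day X-1" and ends with the score of the day after Day X.
- Section 7.2.5.4 compares recovery between arms as an efficacy endpoint and reports "The probability that the true odds ratio is greater than 1".

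The outcome is counted from randomisation:
- Section 7.2.1 sets the on-treatment length of time as "Time from date of randomisation to date of last dose of study treatment".
- Section 7.2.1.1 uses it in the rate model: "An offset to account for the length of time on treatment or in study, depending on the specified time-period, for each participant".
- Section 13.3.2 states: "Exacerbation events during the 12-Week Treatment Period will be classified according to their occurrence from randomisation until treatment discontinuation/study withdrawal days".

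Neither the table entry, Section 7.2.1 nor Appendix 3 sets a landmark, limits the analysis to later events, or adds a caveat.

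**The concern.** Two features combine. First, the strata are formed on an outcome that the drug is intended to change. If it does, some participants who would not have recovered on placebo move into the recovered stratum on active treatment, and each stratum then holds a different mix of patients in the two arms. Second, the counted follow-up begins before the status is known. An early exacerbation is counted as an outcome and may also help decide the stratum.

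The table stands beside subgroup tables defined at baseline, in the same shell. A reader would take its ratios as randomised subgroup effects, at an interim whose stated purpose is to inform internal decisions.

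**Working it through.** The SAP gives no rate, power or effect size for this table, so there is no stated figure to reproduce. The timing follows from the SAP; the sizes need assumptions.

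**Timing (from the SAP).** A recovery day of 14 needs seven rolling averages, for Days 14 to 14 + 6 = 20. The centred average for Day 20 uses the Day 21 diary. Days 1 to 20 are 20/84 = 23.8% of the planned treatment period, and Days 1 to 21 are 21/84 = 25.0%.

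**Event ordering alone, in closed form.** Assume every patient has the same rate of 0.35 per 84 days, that any event in Days 1 to 20 prevents Day 14 recovery, and that the recovery probability is otherwise 0.4 on placebo.
- Probability of recovery on placebo: 0.4 × exp(−0.35 × 20/84) = 0.4 × 0.920 = 0.368.
- Rate in recovered: 0.35 × 64/84 = 0.267, since they have no events in the first 20 days.
- Rate in not recovered: (0.35 − 0.368 × 0.267)/(1 − 0.368) = 0.40.
- The strata differ, 0.27 against 0.40, although all patients carry the same risk.
- On active treatment with recovery odds ratio 2: odds 0.4/0.6 × 2 = 1.333, probability 0.571, and 0.571 × 0.920 = 0.526 after blocking. Rate in not recovered: (0.35 − 0.526 × 0.267)/(1 − 0.526) = 0.44.
- Ratio in not recovered: 0.44/0.40, or 1.11 before rounding. Ratio in recovered: 1.00.

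**With patients differing in risk (simulation).** Assumed: gamma frailty with mean 1 and variance 0.8, frailer patients less likely to recover, and the full 84 days on treatment. The placebo rate is 0.35 per 84 days and the placebo recovery parameter 0.4 unless stated, and an event in Days 1 to 20 blocks recovery unless stated. Most settings used 2,000,000 patients per arm. The ratio is the active rate over the placebo rate within the stratum.

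| Setting | Recovered | Not recovered |
|---|---|---|
| No effect on exacerbations, recovery odds ratio 1 | 1.00 | 1.00 |
| Same, odds ratio 1.5 | 1.06 | 1.07 |
| Same, odds ratio 2 | 1.10 | 1.14 |
| Same, odds ratio 3 | 1.16 | 1.25 |
| Odds ratio 2, placebo recovery parameter 0.6 | 1.09 | 1.19 |
| Odds ratio 2, rate 0.4, recovery parameter 0.5 | 1.07 | 1.18 |
| As the row above, early event does not block recovery | 1.07 | 1.09 |
| Odds ratio 2, no frailty, no blocking | 1.00 | 1.00 |
| True ratio 0.80, odds ratio 1 | 0.81 | 0.80 |
| True ratio 0.80, odds ratio 2 | 0.89 | 0.91 |
| No effect on exacerbations, odds ratio 2, counted only after Day 20 | 1.10 | 1.07 |

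At odds ratio 2, placebo rates of 0.2 or 0.5 give about 1.10 and 1.13 to 1.14. A true 20% reduction shows as 11% and 9%, about half. The last row shows that a landmark removes the event-before-split part but leaves the selection part. It also shows that which stratum lies further from 1 depends on the assumptions.

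**The case against.** Several counter-arguments have force.

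- **Bias is not certain.** A reader might infer that the ratios are biased whatever the drug does. They are not: with no effect on recovery or early exacerbations they stay at 1.00. Even with an effect on recovery, they stay at 1.00 if recovery is unrelated to exacerbation risk and early events do not block it.
- **Blocking is an assumption.** Because the reference peak is taken over the first 14 days, an early flare can raise it and make the 9-point fall easier. A participant can also complete seven sustained days and exacerbate on, say, Day 16, yet still count as recovered. Without blocking, the non-recovered ratio falls from 1.18 to 1.09 in the setting tested.
- **False benefit is not shown.** A reader might infer that the table would make the drug look effective in one group. In these simulations with a recovery odds ratio above 1, any bias runs against the drug, and the two strata differ only modestly.
- **There is no breach of the subgroup list.** Section 5.4.2 does not name this split, but the list is permissive and allows additional subgroups, so absence from it is not a contradiction. Permission does not make a post-randomisation split valid.
- **The reach is limited.** The futility rule uses the overall exacerbation rate at Interim Analysis 2, whose table list does not contain this split. The End of Treatment interim follows the last participant's treatment, so it cannot alter randomisation.

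These points limit the size and consequence of the problem. They do not restore randomisation within the strata.

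**Conclusion.** The point holds in conditional form. Table 2.39 plans active-versus-placebo ratios within strata of a post-randomisation efficacy outcome, while counting events from before that outcome is settled. If the drug affects recovery or early exacerbations, those ratios are not randomised comparisons and can be biased.

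The mechanism follows from the SAP's definitions; the size does not. With no true effect on exacerbations, a recovery odds ratio of 2 and patients differing in risk, the ratios are about 1.07 to 1.10 in recovered and 1.09 to 1.19 in non-recovered participants, and a true 0.80 appears as about 0.9. These are illustrations, not bounds: rate, frailty, its link to recovery, and blocking are all assumed.

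Separately, the recovered versus non-recovered rates are distorted to the extent that early exacerbations prevent recovery, even without any drug effect. The primary FEV₁ analysis and the overall exacerbation analyses are unaffected.

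**What to change.** Drop Table 2.39, or replace it with a descriptive display of rates by arm and recovery status, with no rate ratio, no probability that the ratio is below 1, and no percent reduction. For that display:
- include participants still on treatment at the end of Day 21;
- classify them by recovery day on or before Day 14;
- count events and exposure from Day 22 only, which leaves 84 − 21 = 63 days of the planned period;
- add a footnote that the comparison is not randomised and is conditional on a post-randomisation outcome and on remaining on treatment.

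A landmark alone is not enough, because the selection remains and restricting to those still on treatment adds a second one. That is why the treatment ratio should go. The cost is one table specification; events in the first 21 days are not used in this display. No new data are needed and no other analysis changes.

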13.11.7. Efficacy Figures

13.11.7.1. Efficacy Figures for Interim Analysis 1

Efficacy: Figures					
No.	Population	IDSL / Example Shell	Title	Programming Notes	Deliverable [Priority]
Change from Baseline in Clinic Visit trough FEV₁					
2.1.	MITT	Example 18	Plot of Dose Response Model of Change from Baseline in FEV ₁ at Day 14 Measured Post-bronchodilator		IA1
2.2.	MITT	Example 18	Plot of Dose Response Model of Change from Baseline in FEV ₁ at Day 28 Measured Post-bronchodilator		IA1
2.3.	MITT	Example 18	Plot of Dose Response Model of Change from Baseline in FEV ₁ at Day 56 measured post-bronchodilator		IA1
2.4.	MITT	Example 18	Plot of Dose Response Model of Change from Baseline in FEV ₁ at Day 14 Measured Post-bronchodilator by Index Exacerbation Severity: Moderate		IA1
2.5.	MITT	Example 18	Plot of Dose Response Model of Change from Baseline in FEV ₁ at Day 14 Measured Post-bronchodilator by Index Exacerbation Severity: Severe		IA1
2.6.	MITT	Example 18	Plot of Dose Response Model of Change from Baseline in FEV ₁ at Day 28 Measured Post-bronchodilator by Index Exacerbation Severity: Moderate		IA1
2.7.	MITT	Example 18	Plot of Dose Response Model of Change from Baseline in FEV ₁ at Day 28 Measured Post-bronchodilator by Index Exacerbation Severity: Severe		IA1

13.11.7.2. Efficacy Figures for Interim Analysis 2

Efficacy: Figures					
No.	Population	IDSL / Example Shell	Title	Programming Notes	Deliverable [Priority]
Change from Baseline in Clinic Visit trough FEV ₁					
2.1.	MITT	Example 18	Plot of Dose Response Model of Change from Baseline in FEV ₁ at Day 14 Measured Post-bronchodilator		IA2
2.2.	MITT	Example 18	Plot of Dose Response Model of Change from Baseline in FEV ₁ at Day 28 Measured Post-bronchodilator		IA2
2.3.	MITT	Example 18	Plot of Dose Response Model of Change from Baseline in FEV ₁ at Day 56 Measured Post-bronchodilator		IA2
2.4.	MITT	Example 18	Plot of Dose Response Model of Change from Baseline in FEV ₁ at Day 84 Measured Post-bronchodilator		IA2
2.5.	MITT	Example 18	Plot of Dose Response Model of Change from Baseline in FEV ₁ at Day 14 Measured Post-bronchodilator by Index Exacerbation Severity: Moderate		IA2
2.6.	MITT	Example 18	Plot of Dose Response Model of Change from Baseline in FEV ₁ at Day 14 Measured Post-bronchodilator by Index Exacerbation Severity: Severe		IA2
2.7.	MITT	Example 18	Plot of Dose Response Model of Change from Baseline in FEV ₁ at Day 28 Measured Post-bronchodilator by Index Exacerbation Severity: Moderate		IA2
2.8.	MITT	Example 18	Plot of Dose Response Model of Change from Baseline in FEV ₁ at Day 28 Measured Post-bronchodilator by Index Exacerbation Severity: Severe		IA2
2.9.	MITT	Example 18	Plot of Dose Response Model of Change from Baseline in FEV ₁ at Day 56 Measured Post-bronchodilator by Index Exacerbation Severity: Moderate		IA2

Efficacy: Figures					
No.	Population	IDSL / Example Shell	Title	Programming Notes	Deliverable [Priority]
2.10.	MITT	Example 18	Plot of Dose Response Model of Change from Baseline in FEV ₁ at Day 56 Measured Post-bronchodilator by Index Exacerbation Severity: Severe		IA2
2.11.	MITT	Example 18	Plot of Dose Response Model of Change from Baseline in FEV ₁ at Day 84 Measured Post-bronchodilator by Index Exacerbation Severity: Moderate		IA2
2.12.	MITT	Example 18	Plot of Dose Response Model of Change from Baseline in FEV ₁ at Day 84 Measured Post-bronchodilator by Index Exacerbation Severity: Severe		IA2
2.13.	MITT	Example 31	Plot of Repeated Measures Model of Change from Baseline in FEV ₁ Measured Post-bronchodilator		IA2
2.14.	MITT	Example 31	Plot of Repeated Measures Model of Change from Baseline in FEV ₁ Measured Post-bronchodilator by Index Exacerbation Severity: Moderate		IA2
2.15.	MITT	Example 31	Plot of Repeated Measures Model of Change from Baseline in FEV ₁ Measured Post-bronchodilator by Index Exacerbation Severity: Severe		IA2
Time to Next Exacerbation					
2.16.	MITT	Example 30	Kaplan-Meier Plot of Time to Next On-treatment (Moderate/Severe) Exacerbation		IA2
2.17.	MITT	Example 30	Kaplan-Meier Plot of Time to Next On-treatment (Mild/Moderate/Severe) Exacerbation		IA2

13.11.7.3. Efficacy Figures for End of Treatment Interim Analysis and SAC

Efficacy: Figures					
No.	Population	IDSL / Example Shell	Title	Programming Notes	Deliverable [Priority]
Change from Baseline in Clinic Visit trough FEV ₁					
2.1.	MITT	Example 18	Plot of Dose Response Model of Change from Baseline in FEV ₁ at Day 14 Measured Post-bronchodilator		SAC
2.2.	MITT	Example 18	Plot of Dose Response Model of Change from Baseline in FEV ₁ at Day 28 Measured Post-bronchodilator		SAC
2.3.	MITT	Example 18	Plot of Dose Response Model of Change from Baseline in FEV ₁ at Day 56 Measured Post-bronchodilator		SAC
2.4.	MITT	Example 18	Plot of Dose Response Model of Change from Baseline in FEV ₁ at Day 84 Measured Post-bronchodilator		SAC
2.5.	MITT	Example 18	Plot of Dose Response Model of Change from Baseline in FEV ₁ at Day 14 Measured Post-bronchodilator by Index Exacerbation Severity: Moderate		SAC
2.6.	MITT	Example 18	Plot of Dose Response Model of Change from Baseline in FEV ₁ at Day 14 Measured Post-bronchodilator by Index Exacerbation Severity: Severe		SAC
2.7.	MITT	Example 18	Plot of Dose Response Model of Change from Baseline in FEV ₁ at Day 28 Measured Post-bronchodilator by Index Exacerbation Severity: Moderate		SAC
2.8.	MITT	Example 18	Plot of Dose Response Model of Change from Baseline in FEV ₁ at Day 28 Measured Post-bronchodilator by Index Exacerbation Severity: Severe		SAC
2.9.	MITT	Example 18	Plot of Dose Response Model of Change from Baseline in FEV ₁ at Day 56 Measured Post-bronchodilator by Index Exacerbation Severity: Moderate		SAC

Efficacy: Figures					
No.	Population	IDSL / Example Shell	Title	Programming Notes	Deliverable [Priority]
2.10.	MITT	Example 18	Plot of Dose Response Model of Change from Baseline in FEV ₁ at Day 56 Measured Post-bronchodilator by Index Exacerbation Severity: Severe		SAC
2.11.	MITT	Example 18	Plot of Dose Response Model of Change from Baseline in FEV ₁ at Day 84 Measured Post-bronchodilator by Index Exacerbation Severity: Moderate		SAC
2.12.	MITT	Example 18	Plot of Dose Response Model of Change from Baseline in FEV ₁ at Day 84 Measured Post-bronchodilator by Index Exacerbation Severity: Severe		SAC
2.13.	MITT	Example 31	Plot of Adjusted Posterior Medians (95% HPD CrI) of Change from Baseline in FEV ₁ Measured Post-bronchodilator		EOT, SAC
2.14.	MITT	Example 31	Plot of Adjusted Posterior Medians (95% HPD CrI) of Change from Baseline in FEV ₁ Measured Post-bronchodilator by Index Exacerbation Severity: Moderate		EOT, SAC
2.15.	MITT	Example 31	Plot of Adjusted Posterior Medians (95% HPD CrI) of Change from Baseline in FEV ₁ Measured Post-bronchodilator by Index Exacerbation Severity: Severe		EOT, SAC
Time to Next Exacerbation					
2.16.	MITT	Example 30	Kaplan-Meier Plot of Time to Next On-treatment (Moderate/Severe) Exacerbation		EOT, SAC
2.17.	MITT	Example 30	Kaplan-Meier Plot of Time to Next On-treatment (Mild/Moderate/Severe) Exacerbation		SAC
2.18.	MITT	Example 30	Kaplan-Meier Plot of Time to Next On-or Off-treatment (Moderate/Severe) Exacerbation During the 12-Week Treatment Period		SAC

Efficacy: Figures					
No.	Population	IDSL / Example Shell	Title	Programming Notes	Deliverable [Priority]
2.19.	MITT	Example 30	Kaplan-Meier Plot of Time to Next On-or Off-treatment (Mild/Moderate/Severe) Exacerbation During the 12-Week Treatment Period		SAC
2.20.	MITT	Example 30	Kaplan-Meier Plot of Time to Next (Moderate/Severe) Exacerbation Following Cessation of Study Treatment		SAC

